## **13.3 Planned Analysis**

### **13.3.1 Dose Level Review Team (DLRT)**

Dose Level Review Meetings (DLRMs) will be held by the DLRT to review data, evaluate safety, and make decisions on dose escalation/change. The DLRT will be composed of the investigators or designees, and the following Amgen representatives: medical monitor, global safety officer or designee, clinical study manager, biostatistician and additional members may be added as needed (eg, clinical pharmacologist). The following members are responsible for DLRT decisions: investigators, Amgen medical monitor, and global safety officer or designee. A quorum must be in attendance for the

DLRM. The quorum is defined as > 50% of the participating investigators or their qualified designee (ie, sub-investigator or research nurse or study coordinator possessing written documentation [eg e-mail] of the investigator's vote). All Amgen representatives or designees must be present. The DLRM will be rescheduled if a quorum is not reached.

All available study data, including data collected after the initial DLT window, demographics, investigational product administration, medical history, concomitant medications, adverse events, ECGs, vital signs, laboratory data and PK/█ information will be reviewed. Data will not need to be source data verified and queries will not need to be resolved prior to the DLRM.

Modeling of available potential safety risk data to predict safety risk for dose escalation decisions may also be considered.

### 13.3.2 Primary Analysis

The main objectives of the primary analysis are to determine the MTD for each formulation of oprozomib in combination with pomalidomide and dexamethasone and further evaluate the safety, tolerability and efficacy of the OPomd combination in subjects with relapsed or refractory multiple myeloma. The primary analysis will be based on subject data collected up to two months from the date of last subject enrollment. In addition, this analysis will be used to possibly recommend the most appropriate oprozomib dose and formulation to be tested in future clinical trials in an OPomd combination. The selection of the oprozomib recommended dose and formulation will be based on all data from the escalation cohorts.

Safety and tolerability will be assessed through summaries of study drug administration, DLTs, adverse events, changes in selected laboratory analytes, vital signs, and physical findings by dose level. Means and standard deviations will be used to summarize the total dose for each component of study drug received. All summaries will be presented by the assigned dose level and for all subjects.

All adverse event data will be listed by study site, dose level, subject identification number, and study day. All adverse events will be summarized by preferred term, appropriate thesaurus levels, and CTCAE (Version 4.03) toxicity grade. In addition, all serious adverse events, including deaths, will be listed separately and summarized.

Efficacy analyses of ORR and BOR will be performed using both the efficacy and safety population as defined previously.

### **13.3.3 Final Analysis**

The objective of the final analysis is to provide an update on safety and tolerability, and efficacy results. The statistical methods used in the final analysis will be the same as those employed in the primary analysis. The final analysis will be based on subject data collected through study discontinuation or at the end of the study which includes the 30 day safety follow-up, whichever occurs first.

## **13.4 Planned Methods of Analysis**

### **13.4.1 General Considerations**

All analyses for the study are [REDACTED] and hypothesis generating. Descriptive statistics will be used to summarize most analysis results.

### **13.4.2 Primary Endpoints**

#### **13.4.2.1 Maximum Tolerated Dose**

Refer to Section 9.2.1.2 for a description of the dose escalation method.

The number of DLTs and adverse events at each dose level will be summarized separately for each oprozomib formulation in combination with dexamethasone and in combination with pomalidomide and dexamethasone.

#### **13.4.2.2 Safety Endpoint(s)**

Subject incidence of all treatment emergent adverse events of interest will be tabulated by system organ class and preferred term. Tables of fatal adverse events, serious adverse events, adverse events leading to withdrawal from investigational product, other protocol-required therapies or from study, and adverse events of interest will also be provided. Relevant laboratory and vital sign (temperature, heart rate, respiratory rate, and blood pressure) data will be displayed by visit and time (when available), with CTCAE (Version 4.03) Grade 3 and 4 values identified where appropriate. Additionally, all laboratory data will be summarized by CTCAE Grade.

ECG analyses include summary changes from baseline for ECG intervals, summaries of the proportion of subjects with on-study corrected QT interval (QTc) values that reach certain values (eg, > 450 msec), and summaries of the proportion of subjects with categorical changes from baseline (eg, < 30 msec).

### **13.4.3 Secondary Endpoint(s)**

#### **13.4.3.1 Pharmacokinetic Endpoints**

The PK endpoints include, but are not limited to  $C_{max}$ ,  $t_{max}$ , and  $AUC_{last}$  of oprozomib following dosing on cycle 1 day 8 and cycle 1 day 22.

Blood samples will be collected from all subjects for determination of plasma concentrations of oprozomib at time points specified in the schedule of assessments (Table 6). Individual oprozomib concentration-time data and summary statistics will be tabulated for each dose level. Individual, mean, and standard deviation concentration-time data may be plotted for each dose level.

[figure not shown]
PK parameters will be calculated using non-compartmental methods. Actual dosing and sampling times will be used for calculation of PK parameters. PK parameter estimates will be summarized descriptively. Other pharmacokinetic parameters such as  $AUC_{inf}$ , apparent clearance (CL/F), and terminal half-life ( $t_{1/2}$ ) may be analyzed. Population PK modeling may be performed to better characterize the PK of oprozomib using intense sampling following dosing on cycle 1 day 8 and cycle 1 day 22 and sparse sampling in day 1 of cycles 1, 3 and 5.

#### 13.4.3.2 Efficacy Endpoints

All efficacy assessments will follow IMWG uniform response criteria and be performed every 4 weeks ( $\pm$  1 week).

Overall response rate (defined as the proportion of best overall response of stringent complete response [sCR], complete response [CR], very good partial response [VGPR], and partial response [PR]), best overall response, PFS (defined as the number of months from subject's first study dose date to the earlier of disease progression or death due to any cause), and DOR will be summarized for all subjects overall, by formulation, by dose cohort level, and by formulation and dose cohort level along with 95% confidence intervals when applicable.

All subjects who receive treatment with any amount of the OPomd and have a baseline disease assessment and at least 1 post-baseline disease assessment will be included in the efficacy analyses. Additional efficacy analyses will be performed based on subjects who receive treatment with any amount of OPomd.

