#### **Primary Analysis**

The objectives of the primary analysis are to determine the MTD for each formulation of oprozomib in combination with pomalidomide and dexamethasone and further evaluate the safety and tolerability of the OPomd combination in subjects with relapsed or refractory multiple myeloma. In addition, this analysis will be used, as possible, to recommend the most appropriate oprozomib dose and formulation to be tested in future clinical trials in an OPomd combination, based on safety, tolerability, efficacy, PK and other available data from all the escalation cohorts.

The primary analysis will be based on subject data collected up to two months from the date of last subject enrollment. A Bayesian 2-parameter logistic regression model, the NCRM will be applied to observed DLTs to find MTDs for the oprozomib formulations (Neuenschwander, 2008). The prior distribution and the data available after each dose cohort are applied to the algorithm that computes the posterior distribution of the DLT rate at each dose level. The posterior probabilities of the estimated DLT rate at each dose to fall into target toxicity interval (15% to 25%) or excessive/unacceptable toxicity interval (> 25% to 100%) will be used in the dose escalation decision and the final determination of the MTD. Refer to study design section for a detailed description of the dose escalation method. The safety analyses will be based on the safety evaluable population, which is defined as all subjects who received any amount of the study treatment regimen oprozomib, dexamethasone and pomalidomide. Safety and tolerability will be assessed through summaries of study drug administration, DLTs, adverse events, changes in selected laboratory analytes, and vital signs by dose level.

The primary efficacy analysis will be performed in all subjects that received at least one cycle of OPomd and have baseline disease assessment and at least one post-baseline disease assessment. Both overall response rate and the best overall response will be summarized.

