##### **13.1.2 Analysis Sets**

The safety population is defined as all subjects who receive any amount of oprozomib, pomalidomide and/or dexamethasone.

The efficacy population is defined as subjects who are included in the safety evaluable population, and have a baseline disease assessment and at least 1 post-baseline disease assessment.

PK population is defined as subjects for whom at least 1 PK parameter can be adequately estimated.

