It is defined as the first day that protocol specified study treatment is administered to the subject.

Study Day

Post study day: study day= (date - date of Study Day 1) + 1

Pre study day: study day= (date – date of Study Day 1)

Time to Response (TTR)

Time to response defined as the interval from the first administration of study treatment to the first documentation of confirmed response. Response is defined as any of the following: stringent complete response (sCR), complete response (CR), very good partial response (VGPR), or partial response (PR) (all according to Revised International Myeloma Working Group Uniform Response Criteria [IMWG-URC]).

Time to response is calculated as the number of days:

(date of first response – date of study day 1 +1).

Time to response will be calculated only for subjects with response.

Treatment-Emergent Adverse Event (TEAE)

Treatment-emergent adverse events are events categorized as Adverse Events (AEs) **starting on or after first dose of investigational product as determined by the flag indicating if the adverse event started prior to the first dose on the Events CRF and up to and including 30 days after the last dose of investigational product or the End of Study date, whichever is earlier.**

Treatment-Related AE

A treatment-related AE is any treatment-emergent AE that per investigator review has a reasonable possibility of being caused by study treatment.

Disease-Related Events

Disease-Related Events are events (serious or non-serious) anticipated to occur in the study population due to the underlying disease.

C_{max}

Maximum observed serum concentration.

t_{max}

Time to C_{max}

AUC_{last}

Area under the concentration-time curve from time 0 (time of investigational product administration) to the time of the last quantifiable concentration.

Progression free survival

The number of months from subject's first study dose date to the earlier of disease progression or death due to any cause.

Progression free survival data will be censored as described below:

- **Patients who are alive and do not have documented disease progression at the time of analysis will be censored at the date of the last disease assessment.**
- **Patients who are alive and do not have disease assessment at the time of analysis will be censored at the first study dose date.**

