9.5.2 Analyses of Secondary Efficacy Endpoint(s)

Overall response rate (defined as the proportion of best overall response of stringent complete response [sCR], complete response [CR], very good partial response [VGPR], and partial response [PR]), best overall response, PFS (defined as the number of months from subject's first study dose date to the earlier of disease progression or death due to any cause), and DOR will be summarized for all subjects overall, by formulation, by dose cohort level, and by formulation and dose cohort level along with 95% confidence intervals when applicable.

All subjects who receive treatment with any amount of the OPomd and have a baseline disease assessment and at least 1 post-baseline disease assessment will be included in the efficacy analyses. Additional efficacy analyses will be performed based on subjects who receive treatment with any amount of OPomd.

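### The main PFS set requires a post-baseline disease assessment, so a treated subject who dies before any such assessment is left out of the main analysis instead of being counted as an event.

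*Protocol*

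**What the plan says.** Protocol 13.4.3.2 defines PFS as the "number of months from subject's first study dose date to the earlier of disease progression or death due to any cause". The next paragraph sets the population for the efficacy analyses: "All subjects who receive treatment with any amount of the OPomd and have a baseline disease assessment and at least 1 post-baseline disease assessment". SAP 9.5.2 repeats both; its subjects must "have a baseline disease assessment and at least 1 post-baseline disease assessment will be included in the efficacy analyses". Neither section exempts PFS. Protocol 13.1.2 puts the same requirement in its efficacy population: "have a baseline disease assessment and at least 1 post-baseline disease assessment". Disease assessments are scheduled every 4 weeks, plus or minus 1 week.

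Both sections then add a second population: "Additional efficacy analyses will be performed based on subjects who receive treatment with any amount of OPomd". No endpoint is named there. Where two populations are assigned by endpoint, in Protocol 13.3.2 and SAP 7.2, only response is listed: "Efficacy analyses of ORR and BOR will be performed using both the efficacy and safety population as defined previously". The synopsis gives a stricter set, subjects who "received at least one cycle of OPomd and have baseline disease assessment and at least one post-baseline disease assessment", and again mentions only overall response rate and best overall response.

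The SAP definition of PFS (Section 5) includes this censoring rule: "Patients who are alive and do not have disease assessment at the time of analysis will be censored at the first study dose date". SAP Section 10 declares no changes from the protocol's analyses.

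**The concern.** The PFS clock starts at first dose, but entry to the main set depends on something that happens later, namely having a post-baseline assessment. A subject who dies in between meets the definition of an event and then disappears from both numerator and denominator. Nobody in the main set can die before a first post-baseline assessment, so the early part of the curve is protected by construction.

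The SAP also does not fit together here. Its rule for living subjects with no disease assessment has no use in a set where everyone has one. The rule makes sense only in an all-treated PFS analysis, which the text makes additional and does not tie to PFS.

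PFS is tabulated by formulation, by dose cohort and by both. The OPomd cohorts in Table 2 have 4 to 10 subjects, so one missing death can be visible. Efficacy is also among the data used to recommend a formulation and dose.

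**Working it through.** **1. Who is lost, and in which direction.** Take a treated OPomd subject with no post-baseline assessment.

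- Died: an event under the PFS definition. Omitting it raises the early part of the curve.
- Alive: censored at first dose under SAP Section 5. The subject is not at risk at any later event time, so omitting the subject leaves the Kaplan-Meier curve unchanged.
- Progression documented at any post-baseline assessment: the subject meets the post-baseline requirement. The end-of-study visit repeats SPEP, UPEP and serum free light chain (Protocol 10.2.20), so many early dropouts would qualify.

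The requirement can therefore leave PFS unchanged or overstate it, and only through deaths.

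**2. How many subjects are outside the set so far.** Inputs are from Protocol 5.5.5 and Table 2.

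| | Treated | Evaluable | Not evaluable |
|---|---|---|---|
| IR OPomd | 4 + 8 + 10 + 8 = 30 | 28 | 2 |
| GR OPomd | 4 + 5 = 9 | 8 | 1 |
| All OPomd | 39 | 36 | 3 (3/39 = 7.7%) |

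The protocol does not state 36 of 39; it is inferred from two places. Section 5.5.5 gives 45 evaluable subjects, described as 9 with dexamethasone and 23 with pomalidomide and dexamethasone, but 9 + 23 = 32. The response denominators do give the total: 9 + 28 + 8 = 45. The 23 matches the responders, 20 + 3. The inference also assumes that the 36 evaluable subjects come from the 39 in the Table 2 OPomd columns.

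**3. How many of the three could be deaths.** Table 2 shows no fatal adverse event and no fatal disease-related event in any IR OPomd cohort. GR 200 mg (N = 5) has one fatal adverse event and one fatal disease-related event; GR 150 mg has none. Treatment-emergent adverse events run to 30 days after last dose or end of study, whichever is earlier, and fatal disease-related events must be reported through the end-of-study visit (Protocol 12.2.1). That covers nearly any on-study death before a week-4 assessment. Only one GR subject is non-evaluable, so the tabulated data support at most about one omitted early death.

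**4. Effect if that GR subject was an early death.** PFS just after the death is (number at risk − 1) / (number at risk).

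- GR, all treated: 8/9 = 88.9%; main set: 8/8 = 100%.
- All OPomd, with the two IR subjects alive and censored at first dose: 36/37 = 97.3%; main set: 36/36 = 100%.

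**5. Effect on the median (illustration).** Assume exponential PFS with median m in all treated subjects, and remove a fraction q as early deaths. The remaining curve is S(t)/(1 − q), so its median is m × ln[0.5(1 − q)] / ln(0.5).

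- All OPomd, q = 1/39: 3.7% longer.
- GR, q = 1/9: 17.0% longer.

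With m = 4.0 months, the background figure in Protocol 5.5.4.3, these medians become 4.15 and 4.68 months.

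**The case against.** The best defence is that the plan already covers this. The sentence on additional analyses in everyone who received any OPomd follows directly after PFS is listed and is not restricted by endpoint. The first-dose censoring rule is useful mainly in such an analysis, which suggests that one was intended. On that reading the only question is which of two planned displays is labelled main. PFS is also a descriptive secondary endpoint in a non-randomised phase 1b study with no PFS hypothesis, and one subject is minor against sampling error in cohorts this small.

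Much of this stands, and it limits the size of the point. It does not remove it: PFS is not named for the all-treated set, and the sections that assign two populations by endpoint list response only.

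A reader might infer more than the documents support, in two ways. First, that all three non-evaluable subjects were early events, so that IR PFS would fall to 28/30 = 93%. Table 2 shows no fatal event in any IR OPomd cohort, so this is not supported. Second, that early toxicity or early treatment failure in general is removed from PFS. It is not: documented progression meets the assessment requirement, and a living unassessed subject adds no event under the SAP's own rule.

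**Conclusion.** The point holds, for deaths only and at modest size. The main set drops a class of subjects whom the PFS definition counts as events, and the resulting bias has one direction.

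Whether any death has actually been dropped is unknown. The documents do not say why the three subjects were not evaluable, and they give neither the timing of the GR 200 mg fatal events nor whether those subjects were evaluable. The 89% and 97% figures are conditional on the excluded GR subject having died before any post-baseline assessment. They also rest on the inferred 36 of 39 and on Table 2 capturing early deaths; a death more than 30 days after a very early last dose, or after leaving the study, could be missed. If the excluded GR subject was alive and unassessed, the two sets give the same curve in these data.

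**What to change.** In Protocol 13.4.3.2 and SAP 9.5.2:

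- Name all subjects who received any OPomd as the main set for PFS.
- State that a death before the first post-baseline assessment is an event on the date of death.
- Keep the existing censoring rules in SAP Section 5, including censoring at first dose for living subjects with no assessment.
- Keep the assessment-based set as the additional PFS analysis.
- Leave the ORR and BOR sets as they are.

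No new data are needed, and an all-treated efficacy run is already foreseen, so the work is mainly wording. PFS may look slightly shorter. A primary analysis cutoff has already passed (Table 2 reports data to 02 December 2019), so the change should be reported openly as an amendment that applies to the final analysis.

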## **14. REGULATORY OBLIGATIONS**

### **14.1 Informed Consent**

An initial sample informed consent form is provided for the investigator to prepare the informed consent document to be used at his or her site. Updates to the template are to be communicated formally in writing from the Amgen Study Manager to the investigator. The written informed consent form is to be prepared in the language(s) of the potential subject population.

Before a subject's participation in the clinical study, the investigator is responsible for obtaining written informed consent from the subject after adequate explanation of the aims, methods, anticipated benefits, and potential hazards of the study and before any protocol specific screening procedures or oprozomib is administered.

The investigator is also responsible for asking the subject if the subject has a primary care physician and if the subject agrees to have his/her primary care physician informed of the subject's participation in the clinical study. If the subject agrees to such notification, the investigator is to inform the subject's primary care physician of the subject's participation in the clinical study. If the subject does not have a primary care physician and the investigator will be acting in that capacity, the investigator is to document such in the subject's medical record. The acquisition of informed consent and the subject's agreement or refusal of his/her notification of the primary care physician is to be documented in the subject's medical records, and the informed consent form is to be signed and personally dated by the subject and by the person who conducted the informed consent discussion. The original signed informed consent form is to be

---

retained in accordance with institutional policy, and a copy of the signed consent form is to be provided to the subject.

If a potential subject is illiterate or visually impaired and does not have a legally acceptable representative, the investigator must provide an impartial witness to read the informed consent form to the subject and must allow for questions. Thereafter, both the subject and the witness must sign the informed consent form to attest that informed consent was freely given and understood. [Refer to ICH GCP guideline, Section 4.8.9.]

